7.5.2 Reporting of Pregnancy and Lactation to Merck and BIPI

Although pregnancy and lactation are not considered adverse events, it is the responsibility of investigators or their designees to report any pregnancy or lactation in a subject (spontaneously reported to them) that occurs during the trial.

Pregnancy and lactations that occur after the consent form is signed but before treatment allocation must be reported by the investigator if they cause the subject to be excluded from the trial, or are the result of a protocol-specified intervention, including but not limited to washout or

discontinuation of usual therapy, diet, placebo treatment or a procedure.

Pregnancies and lactations that occur from the time of treatment allocation through 120 days following cessation of treatment, or 30 days following the cessation of treatment if the subject initiates new anticancer therapy, whichever is earlier must be reported by the investigator. All reported pregnancies must be followed to the completion/termination of the pregnancy.

Pregnancy outcomes of spontaneous abortion, missed abortion, benign hydatidiform mole, blighted ovum, fetal death, intrauterine death, miscarriage and stillbirth must be reported as serious events (Important Medical Events). If the pregnancy continues to term, the outcome (health of infant) must also be reported. Report pregnancy to BIPI only if it is associated with the SAE (including an outcome that meets SAE criteria).

Such events must be reported within 2 working days to Merck Global Safety. (Attn: Worldwide Product Safety; [contact]) as well as Boehringer Ingelheim.

7.5.3 Immediate Reporting of Adverse Events to Merck and BIPI

7.5.3.1 Serious Adverse Events

A serious adverse event is any adverse event occurring at any dose or during any use of Merck's product that:

- Results in death;
- Is life threatening;
- Results in persistent or significant disability/incapacity;
- Results in or prolongs an existing inpatient hospitalization;
- Is a congenital anomaly/birth defect;
- Is another important medical event

Note: In addition to the above criteria, adverse events meeting either of the below criteria, although not serious per ICH definition, are reportable to the Merck in the same timeframe as SAEs to meet certain local requirements. Therefore, these events are considered serious by Merck for collection purposes.

- Is a new cancer (that is not a condition of the study);
- Is associated with an overdose.

Refer to Table 12.7 for additional details regarding each of the above criteria.

For the time period beginning when the consent form is signed until treatment allocation, any serious adverse event, or follow up to a serious adverse event, including death due to any cause other than progression of the cancer under study (Section 7.2.3.3 for additional details) that occurs to any subject must be reported within 2 working days to Merck Global Safety if it causes the subject to be excluded from the trial, or is the result of a protocol-specified intervention, including but not limited to washout or discontinuation of usual therapy, diet, placebo treatment

or a procedure.

Progression of the cancer under study is not considered an adverse event unless it results in hospitalization or death.

For the time period beginning at treatment allocation, through 90 days following cessation of treatment, or 30 days following cessation of treatment if the subject initiates new anti-cancer therapy, whichever is earlier, any serious adverse event, or follow up to a serious adverse event, including death due to any cause other than progression of cancer under study (reference Section 7.5.4 for additional details), whether or not related to Merck product, must be reported within 2 working days to Merck Global Safety.

Additionally, any serious adverse event, considered by an investigator who is a qualified physician to be related to Merck product that is brought to the attention of the investigator at any time following consent through the end of specified safety follow-up period specified in the paragraph above, or at any time outside of the time period specified in the previous paragraph also must be reported immediately to Merck Global Safety.

SAE reports and any other relevant safety information are to be forwarded to the Merck Global Safety [contact]

Assessment of safety laboratory parameters

A copy of all 15 Day Reports and Annual Progress Reports is submitted as required by FDA, European Union (EU), Pharmaceutical and Medical Devices agency (PMDA) or other local regulators. Investigators will cross reference this submission according to local regulations to the Merck Investigational Compound Number (IND, CSA, etc.) at the time of submission. Additionally investigators will submit a copy of these reports to Merck & Co., Inc. (Attn: Worldwide Product Safety; [contact]) at the time of submission to FDA.

All subjects with serious adverse events must be followed up for outcome.

The investigator shall report all SAEs and non serious AEs relevant to a reported SAE by fax from the time the informed consent is signed until the trial specified observational period (please specify) using BI IIS SAE form to BIPI Unique Entry Point in accordance with the following timelines:

- within five (5) calendar days upon receipt of initial and follow-up SAEs containing at least one fatal or immediately life-threatening event;
- within ten (10) calendar days upon receipt of any other initial and follow-up SAEs.

BI Unique Entry point:

Boehringer Ingelheim Pharmaceuticals, Inc
[name]
[name]

[contact]

7.5.3.2 Events of Clinical Interest

Selected non-serious and serious adverse events are also known as Events of Clinical Interest (ECI) and must be reported within 2 working days to Merck Global Safety. (Attn: Worldwide Product Safety; [contact])

For the time period beginning when the consent form is signed until treatment allocation, any ECI, or follow up to an ECI, that occurs to any subject must be reported within 2 working days to Merck Global Safety if it causes the subject to be excluded from the trial, or is the result of a protocol-specified intervention including but not limited to washout or discontinuation of usual therapy, diet, placebo treatment or a procedure.

For the time period beginning at treatment allocation through 90 days following cessation of treatment, or 30 days following cessation of treatment if the subject initiates new anticancer therapy, whichever is earlier, any ECI, or follow up to an ECI, whether or not related to Merck product, must be reported within 24 hours to Merck Global Safety.

Events of clinical interest for this trial include:

1. an overdose of Merck product, as defined in Section 7.2.1 - Definition of an Overdose for This Protocol and Reporting of Overdose to Merck, that is not associated with clinical symptoms or abnormal laboratory results.
2. an elevated AST or ALT lab value that is greater than or equal to 3X the upper limit of normal and an elevated total bilirubin lab value that is greater than or equal to 2X the upper limit of normal and, at the same time, an alkaline phosphatase lab value that is less than 2X the upper limit of normal, as determined by way of protocol-specified laboratory testing or unscheduled laboratory testing.*

***Note:** These criteria are based upon available regulatory guidance documents. The purpose of the criteria is to specify a threshold of abnormal hepatic tests that may require an additional evaluation for an underlying etiology.

7.5.4 Protocol-Specific Exceptions to Serious Adverse Event Reporting

Efficacy endpoints as outlined in this section will not be reported to Merck as described in Section 7.5.3 .- Immediate Reporting of Adverse Events to Merck and BAPI, unless there is evidence suggesting a causal relationship between the drug and the event. Any such event will be submitted to Merck Global Safety within 2 working days either by electronic or paper media. Specifically, the suspected/actual events covered in this exception include any event that is disease progression of the cancer under study.

The Sponsor will monitor unblinded aggregated efficacy endpoint events and safety data to

ensure the safety of the subjects in the trial. Any suspected endpoint which upon review is not progression of the cancer under study will be forwarded to Merck Global Safety as a SAE within 2 working days of determination that the event is not progression of the cancer under study

All the reports specified in this section will also be submitted to BIPI according to SAE reporting timeframe in section 7.5.3.1.

Hospitalization related to convenience (e.g. transportation issues etc.) will not be considered a SAE.

7.5.5 Evaluating Adverse Events

An investigator who is a qualified physician will evaluate all adverse events according to the NCI Common Terminology for Adverse Events (CTCAE), version 4.0. Any adverse event which changes CTCAE grade over the course of a given episode will have each change of grade recorded on the adverse event case report forms/worksheets.

All adverse events regardless of CTCAE grade must also be evaluated for seriousness.

7.5.6 Sponsor-Investigator Responsibility for Reporting Adverse Events

All Adverse Events will be reported to regulatory authorities, IRB/IECs and investigators in accordance with all applicable laws and regulations.

7.5.7 Safety Reporting Requirements for IND Exempt Studies

For Investigator Sponsored IND Exempt Studies there are some reporting requirements for the FDA in accordance with the guidance set forth in 21 CFR 314.80.

Post-marketing 15-Day ‘Alert Report’

The Sponsor-Investigator is required to notify the FDA of each adverse drug experience that is both serious and unexpected and is assessed by the investigator to be possibly related to study treatment as soon as possible but in no case later than 15 calendar days of initial receipt of the information. An unexpected adverse event is one that is not already described in the Investigator Brochure. Such reports (2 copies) are to be submitted to the FDA at the following address: Central Document Room, [name].

All 15-Day Alert Reports submitted to the FDA by the Sponsor-Investigator must also be faxed to Merck.

8.0 STATISTICAL ANALYSIS PLAN

8.1 Statistical Analysis Plan Summary

This is a phase I/Ib study. A minimum of 9 patients, if trial is terminated early due to unacceptable toxicity and a maximum of 38 patients (18 patients in the dose de-escalation cohort plus 10 in each of the two expansion cohorts) are anticipated for this trial. Analysis of safety and biomarkers will be limited to patients who receive active treatment.

The dose de-escalation phase will establish a MTD recommended dose of MK-3475 in combination with lead in MK-3475 followed by the combination or concurrent afatinib/MK-3475.

We plan to enter 3 patients at Dose Level 0. If 0/3 or 1/3 patients experience a DLT on level 0, an additional 3 patients will be accrued to Level 0, where 2 or more DLTs will terminate that study arm and we will proceed to dose level -1.

If 2 or more patients have DLTs at level 0, patients will be accrued at level -1. If 1/3 patients experience a DLT on level -1, an additional 3 patients will be accrued to Level -1, where 2 or more DLTs will require termination of that study arm while 1 DLT out of 6 will result in proceeding with dose level -1 as the MTD for the dose expansion cohorts.

If 2 or more patients have DLTs at level -1, patients will be accrued at level -2. If 1/3 patients experience a DLT on level -2, an additional 3 patients will be accrued to Level -2, where 2 or more DLTs will require termination of the study while 1 DLT out of 6 will result in proceeding with dose level -2 as the MTD for the dose expansion cohorts.

The phase I de-dose escalation portion of the trial will be closed when the maximum tolerated dose level (MTD) or dose level 0 is reached and six patients have been treated at that dose level.

Please see section 5.1.4.2 for further details.

All patients at a given dose level who have not experienced DLT, must be observed for a minimum of 21 days or until completion of their first cycle of therapy before the dose level can be escalated. Treatment will continue in an individual patient at the same dose level if no DLT is observed and if benefit is observed. There will be no dose escalation allowed for an individual patient.

The recommended phase II dose (RP2D) will be determined by the overall assessment of the MTD and toxicities observed in the de-dose escalation and dose expansion portion of this study.

The baseline assumption is that single agent afatinib yields a response rate of 10% in this setting, and a response rate of 10% or less would not warrant further study. A response rate of 40% or greater would justify further study with a larger sample size. With 10 patients enrolled in cohort A expansion arm, we will declare this combination lacking promise if fewer than 3 patients respond, and potentially worthy of further study if 3 or more patients respond. If the true response rate is 10%, the chance of having 3 or more patients respond is 7%. If the true response rate is 40%, the

chance of having 3 or more patients respond is 83%.

If 3 or more patients respond, the response rate, toxicity, and progression-free survival will be evaluated to decide if larger randomized studies are warranted in this disease. Descriptive summaries will be provided for each of these summary measures (numbers and proportion responding, number and proportion with specific type and grade of toxicities, Kaplan-Meier plot and life-table summary of progression-free survival.) As stated earlier, a “pick the winner” approach between cohort A and cohort B based on toxicity: RR, PFS and changes in PDL1 expression will decide which dosing scheme to take further. It is assumed that a true RR >40% would be sufficient to recommend such development, provided safety and tolerability are also acceptable.

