5.1.2 Subject Inclusion Criteria

In order to be eligible for participation in this trial, the subject must:

1. Be willing and able to provide written informed consent for the trial.
2. Be \geq 18 years of age on day of signing informed consent.
3. Have a life expectancy of at least 3 months.
4. Have measurable disease based on RECIST 1.1.
5. Adequate archival tissue for determination of EGFR-mutation status and PD-L1 status with leftover cell block (or equivalent) for additional immune correlates from a tumor lesion biopsied in the last 60 days (prior to signed consent) that has not been previously irradiated occurring: 1) after progression on erlotinib and no intervening systemic treatment between biopsy and initiation of MK-3475 and afatinib or amenable to repeat biopsy.

If inadequate archival tissue as above, patients must be willing to consent for biopsy at baseline and an on treatment biopsy. Patients must also have a tumor in a location that in the opinion of the investigator that is amenable to biopsy or have provided tissue for PD-L1 and other biomarker analysis from a newly obtained formalin fixed tumor tissue from a recent biopsy of a tumor lesion not previously irradiated. No systemic antineoplastic therapy may be administered between the PD- L1 biopsy and initiating study medication. Fine needle aspirates are not acceptable. Core needle or excisional biopsies, or resected tissue is required.

6. Have a performance status of 0 or 1 on the ECOG (Zubrod) Performance Scale.
7. There is no limit to the number of prior treatments for this phase I trial.
8. Demonstrate adequate organ function as defined in Table 2, all screening labs should be

performed within 10 days of treatment initiation.

Table 2 Adequate Organ Function Laboratory Values

System	Laboratory Value
Hematological	
Absolute neutrophil count (ANC)	>1,500 /mcL
Platelets	>100,000 / mcL
Hemoglobin	>9 g/dL, or >5.6 mmol/L
Renal	
Serum creatinine OR Measured or calculated ^a creatinine clearance (GFR can also be used in place of creatinine or CrCl)	$\leq 1.5 \times$ upper limit of normal (ULN) OR ≥ 60 mL/min for subject with creatinine levels $> 1.5 \times$ institutional ULN
Heatic	
Serum total bilirubin	$< 1.5 \times$ ULN
	Direct bilirubin \leq ULN for subjects with total bilirubin levels > 1.5 ULN
AST (SGOT) and ALT (SGPT)	$\leq 2.5 \times$ ULN OR $< 5 \times$ ULN for subjects with liver metastases
Coagulation	

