5.1.4 Trial Treatments

The treatment to be used in this trial is outlined below in Table 3. Each cycle is 21 days in length.

Table 3 Trial Treatments

Drug	Dose/Potency	Dose Frequency	Route of Administration	Regimen/Treatment Period	Use
MK-3475	200 mg	Q3W	IV infusion	Day 1 of each cycle	Experimental

Afatinib*	20 mg, 30 mg, or 40 mg	Once daily	Oral	Day 1-21 of each cycle	Experimental
The MK-3475 dosing interval may be increased due to toxicity as described in Section 5.1.5.3.					
*Cohort B begins in Cycle 3					

Table 4: Dose De- Escalation Schema

Dose Level	Number of Patients	Afatinib (Daily)	MK-3475 (q3 weeks)
0	3+	40 mg D1	200 mg D1
-1	3+	30 mg D1	200 mg D1
-2	3+	20 mg D1	200 mg D1

Each cycle is 21 days in length.

Dose De-Escalation

This treatment will start at dose level 0 (Bold). Afatinib is an oral agent that will be given once daily for 21 days per cycle starting on day 1 of each cycle before administration of MK-3475. It should be taken in the morning with 200 mL of water. Tablets should be taken 1 hour before or 2 hours after meals. MK-3475 will be given once every 3 weeks at a fixed dose of 200 mg. Treatment will be administered until progression or toxicity or withdrawal of consent as defined in this protocol.

Cohort A (Arm A): Dose Expansion

This treatment will start at the MTD determined in the dose de-escalation portion of this trial. Afatinib is an oral agent that will be given once daily for 21 days per cycle starting on day 1 of each cycle before administration of MK-3475. It should be taken in the morning with 200 mL of water. Tablets should be taken 1 hour before or 2 hours after meals. MK-3475 will be given once every 3 weeks. Treatment will be administered until progression or toxicity or withdrawal of consent as defined in this protocol.

Cohort B (Arm B): Dose Expansion

This treatment will start at the MTD determined in the dose de-escalation portion of this trial. MK-3475 will be administered on Day 1 of each cycle, which is q21d in length. Afatinib is an oral agent that will be given once daily for 21 days per cycle starting on Cycle 3 Day 1 of each cycle starting prior to administration of MK-3475 on day 1. It should be taken in the morning with 200 mL of water. Tablets should be taken 1 hour before or 2 hours after meals. MK-3475 will be given once every 3 weeks. Treatment will be administered until progression or toxicity or withdrawal of consent as defined in this protocol.

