5.1.5.2 Dose De-Escalation

Dose Level	Number of Patients	Afatinib (Daily)	MK-3475 (q3 weeks)
0	3+	40 mg D1	200 mg D1
-1	3+	30 mg D1	200 mg D1
-2	3+	20 mg D1	200 mg D1

Figure 1: Dose De-Escalation Schema

This is a phase I study. A minimum of 9 patients (if trial is terminated early due to unacceptable toxicity and a maximum of 38 patients (18 patients in the dose- de-escalation cohort plus 10 in each of the two expansion cohorts) are anticipated for this trial. Analysis of safety and biomarkers will be limited to patients who receive active treatment.

The dose-de-escalation phase will establish a MTD recommended dose of MK-3475 in expansion cohorts (A +B).

We plan to enter 3 patients at Dose Level 0. If 0/3 or 1/3 patients experience a DLT on level 0, an additional 3 patients will be accrued to Level 0, where 2 or more DLTs will terminate that study arm and we will proceed to dose level -1.

If 2 or more patients have DLTs at level 0, patients will be accrued at level -1. If 1/3 patients experience a DLT on level -1, an additional 3 patients will be accrued to Level -1, where 2 or more DLTs will require termination of that study arm while 1 DLT out of 6 will result in proceeding with dose level -1 as the MTD for the dose expansion cohorts.

If 2 or more patients have DLTs at level -1, patients will be accrued at level -2. If 1/3 patients experience a DLT on level -2, an additional 3 patients will be accrued to Level -2, where 2 or more DLTs will require termination of the study while 1 DLT out of 6 will result in proceeding with dose level -2 as the MTD for the dose expansion cohorts.

The phase I dose de-escalation portion of the trial will be closed when the maximum tolerated dose level (MTD) or dose level 0 is reached and six patients have been treated at that dose level.

Dose modifications for patients that experience DLT is described in section 5.1.5.3. Once the dose is decreased, there will be no dose re-escalation allowed for an individual patient.

The recommended phase II dose (RP2D) will be determined by the overall assessment of the MTD and toxicities observed in the de-dose escalation and dose expansion portion of this study.

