5.2 Treatment Allocation

Patients will be enrolled into the dose de-escalation protocol until the MTD is reached. Then patients will be enrolled into 2 cohorts for the dose expansion at the recommended expansion dose and RP2D. Cohort (Arm) A: will be concurrent MK-3475 + afatinib at initiation of treatment and Cohort (Arm) B: will be lead in MK-3475 for 2 cycles followed by concurrent MK-3475 and afatinib. The recommended dose for the dose expansion cohorts and RP2D dose will be informed by the MTD determined in the de-dose escalation phase and assessment of the overall toxicity at the treated dose levels.

After the expansion dose (MTD) is determined, for the expansion phase we will enroll and complete Cohort A: Afatinib + MK-3475 (Concurrent) to further define toxicities at the MTD in the dose expansion. After completion of Cohort A, we will enroll patients into Cohort B (lead-in MK-3475 followed by combination afatinib and MK-3475 commencing at cycle #3).

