2. In general, the window for each visit is \pm 3 days unless otherwise specified.
3. For women of reproductive potential, a urine or serum pregnancy test will be performed within 72 hours prior to first dose of trial treatment. If urine pregnancy results cannot be confirmed as negative, a serum pregnancy test, performed by the local study site laboratory, will be required. Pregnancy tests (serum and/or urine tests) should be repeated if required by local guidelines.
4. Coagulation factors (PT/INR and aPTT) should be monitored closely throughout the trial for any subject receiving anticoagulant therapy.
5. Laboratory tests for screening are to be performed within 10 days prior to the first dose of trial treatment.
6. After Cycle 1, lab samples can be collected up to 72 hours prior to the scheduled time point. Laboratory results must be known and acceptable prior to dosing.
7. The initial tumor imaging will be performed within 30 days prior to the first dose of trial treatment. Scans performed as part of routine clinical management are acceptable for use as the screening scan if they are of diagnostic quality and performed within 30 days prior to the first dose of trial treatment. On-study imaging will be performed every 6 weeks (42 -7 days) after the first dose of trial treatment or more frequently if clinically indicated. The timing for imaging studies should follow calendar days and should not be adjusted for delays in cycle starts or extension of MK-3475/afatinib cycle frequencies. The same imaging technique should be used in a subject throughout the trial. CT including the chest, abdomen and pelvis or PET-CT is required for the baseline assessment.
8. Provide documentation of the subject's tumor EGFR mutation from a CLIA certified laboratory.
9. MK-3475 can be administered for up to 2 years. For the dose de-escalation and Cohort (Arm) A (concurrent afatinib and MK-3475) both drugs will be administered as outlined in this protocol starting with cycle #1. For cohort B. MK-3475 will be initiated with cycle #1 and afatinib will commence in combination with MK-3475 starting with cycle #3.
10. Tumor biopsy for immune and EGFR biomarker analysis will be performed prior to Cycle 1 of treatment either on archival tissue or fresh biopsy (within 60 days). Repeat biopsy will be performed prior to initiation of cycle 3 (42 days (-7 days))

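### Should the go/no-go rule on response also count the six de-escalation patients treated at the expansion dose?

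*Combined protocol and SAP*

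**What the plan says.** Section 8.1 takes a 10% response rate as not worth pursuing and 40% as justifying a larger study. The rule is "With 10 patients enrolled in cohort A expansion arm, we will declare this combination lacking promise if fewer than 3 patients respond"; three or more responders make it potentially worth further study. The plan gives a 7% chance of reaching three at a true 10%, and 83% at a true 40%. Section 3.2 makes efficacy a secondary objective, to be assessed only in a preliminary way.

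De-escalation closes (Section 5.1.5.2, repeated in 8.1) once the MTD or level 0 is reached and "six patients have been treated at that dose level". For Cohort A, Section 5.1.4 says "This treatment will start at the MTD determined in the dose de-escalation portion of this trial". Footnote 9 of the flow chart (Section 6.1) puts both groups on the two drugs from the first cycle: "For the dose de-escalation and Cohort (Arm) A (concurrent afatinib and MK-3475) both drugs will be administered as outlined in this protocol". Section 5.1.2 requires every patient to "Have measurable disease based on RECIST 1.1". Section 5.2 is looser on dose: the expansion dose "will be informed by the MTD determined in the de-dose escalation phase and assessment of the overall toxicity at the treated dose levels".

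The response threshold does not count the de-escalation patients.

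**The concern.** Six patients appear to have the same regimen, dose, entry criteria and response assessment as the ten in Cohort A, yet the rule that judges the combination leaves them out. With so few patients, six more matter. At a true 40% response rate the plan's rule calls an active combination unpromising in 16.7% of trials (1 − 0.8327). If the six could be added with no further recruitment and no rise in false-go, that risk would fall to 6.5% (1 − 0.9349). The plan would then be discarding information it already has, and a useful signal could be misjudged.

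**Working it through.** **Inputs.** From Section 8.1: null rate 10%, target rate 40%, n = 10, cut-off 3. From Section 5.1.5.2: six patients at the selected level. The response rates assumed below for the six, where they differ from Cohort A, are not in the documents.

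**1. The plan's own figures.** With X ~ Bin(10, p), P(X ≥ 3) = 1 − P(0) − P(1) − P(2).

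- p = 0.10: 1 − 0.3487 − 0.3874 − 0.1937 = 0.0702, stated as 7%.
- p = 0.40: 1 − 0.0060 − 0.0403 − 0.1209 = 0.8327, stated as 83%.

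Both reproduce.

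**2. The pooled rule with equal rates.** With X + Y ~ Bin(16, p), P(X + Y ≥ 4) is 0.0684 at p = 0.10 and 0.9349 at p = 0.40. Against the plan's rule, at p = 0.40 a share of 0.1122 of trials move from no-go to go and 0.0100 move the other way. Check: 0.8327 + 0.1122 − 0.0100 = 0.9349.

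**3. The pooled rule with unequal rates.** Let Y ~ Bin(6, q) for the six and X ~ Bin(10, p) for Cohort A. Then P(go) = Σ P(Y = y) · P(X ≥ 4 − y), summed over y = 0 to 6.

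| Cohort A rate p | Rate in the six q | Pooled ≥4/16 | Plan ≥3/10 |
|---|---|---|---|
| 40% | 40% | 93.5% | 83.3% |
| 40% | 30% | 88.8% | 83.3% |
| 40% | 20% | 82.2% | 83.3% |
| 40% | 10% | 73.3% | 83.3% |
| 10% | 10% | 6.8% | 7.0% |
| 10% | 15% | 11.2% | 7.0% |
| 10% | 20% | 16.6% | 7.0% |

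The break-even points are q = 21.4% when Cohort A is at 40%, and q = 10.2% when Cohort A is at 10%. There is some room on the power side. On the false-go side there is almost none: the pooled rule exceeds the plan's error once the six respond only slightly better than the null.

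**4. What a pooled go can mean.** Four responders among 16 can be reached with fewer than three in Cohort A, where the plan would say no-go. At p = q = 0.10 this happens with probability 0.0287. The verdict would then depend on dose-finding patients, at a level retained because few of them had DLTs.

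**5. Whether there are six.** At level 0 the plan adds three patients after 0/3 or 1/3 DLTs. At level −1 the only expansion step written is "If 1/3 patients experience a DLT on level -1, an additional 3 patients will be accrued to Level -1", and level −2 is parallel. The step after 0/3 is not stated there, although the closing rule asks for six. With three patients at the level (n = 13), a cut-off of 4 gives 3.4% false-go and 83.1% power, and a cut-off of 3 gives 13.4% false-go. Neither is a useful gain.

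**6. Whether pooling could be pre-specified cleanly.** The trial is open-label (5.1.7) and the investigator reads response (7.1.2.6). Scans come every six weeks, de-escalation patients continue treatment if they benefit (8.1), and the investigator and coordinator meet at least monthly to discuss patient data (10.5). The protocol is already Version 3.0. The documents do not give accrual status, so whether de-escalation responses have been seen is unknown. If they have, pooling is no longer a pre-specified choice and the plan's rule has to stay. A plan holding both rules, with a partly discretionary switch between them, carries its own risk. If either rule could deliver a go after the data were seen, false-go at 10% would be 0.0702 + 0.0287 = 0.0989, or 9.9%, against 7.0% for the single rule.

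**The case for a change.** The strongest case for pooling is that Section 8.1 sets a formal threshold leading towards larger randomized studies, so it deserves the most efficient rule available. Under equal rates the gain is about ten points of power with slightly lower false-go. It also holds up better when patients are not re-evaluated. With one such patient counted as a non-responder, the pooled rule keeps 90.9% power against 76.8%; with two, 87.6% against 68.5%. A fallback to 3 of 10 could cover a different expansion dose, fewer than six patients, or responses already known, and Cohort A could always be reported separately.

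The arithmetic stands, and under its conditions pooling would be a defensible design. Those conditions are not secured by the documents. Section 5.2 lets the expansion dose depart from the MTD. Sections 1.0 and 3.1 describe progression on erlotinib, while 2.1 and 5.1.1 also admit gefitinib and osimertinib; the documents do not show which wording governed the de-escalation patients, so equal response rates cannot be taken for granted. The change is also more than a sentence: it needs a fixed response set, a rule for replaced patients (5.9), a change to the evaluability definition in 7.1.2.6 and a fallback. It would leave two response rates for one regimen, because the comparison with Cohort B would still use Cohort A's ten.

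**Conclusion.** The concern does not hold. The plan's rule is correctly calculated, clearly stated and adequate for a preliminary secondary aim. The ten-point power gain from pooling is real only if the six respond at Cohort A's rate, received Cohort A's dose, number six, and have responses not yet seen when the rule is fixed. Outside those conditions the pooled rule can do worse than the plan: 73.3% power or 16.6% false-go at the ends of the range shown.

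Little hangs on the label. Three or more responders only open a further look at response, toxicity and progression-free survival, and the documents do not make a low count stop Cohort B: "After completion of Cohort A, we will enroll patients into Cohort B". The six are outside the threshold only. The descriptive summaries in 8.1 are not stated to be limited to Cohort A, so nothing bars reporting the six patients' responses. Keeping dose-finding patients out of the decision is a trade-off on which reasonable statisticians differ, and the plan's choice needs no correction.
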